Dispense/Return Horizon System				X						X d		X
Complaints/device deficiencies				X e	X e	X e	X e	X e	X e	X e	X e	X e
Device uploads/Data review				X	X	X	X	X	X	X	X	X

Abbreviations: S=Screening; ST1=Standard Therapy Day One; ST2=Standard Therapy Day Two; HCL=Hybrid Closed-loop; EW=Early Withdrawal; QC=Quality Control Testing; Hotel/Rental House=HRH; UV=Unscheduled Visit

aEarly withdrawal visit will only be conducted for any subjects that started but did not complete the full study to include standard therapy and the hybrid closed-loop phase.

bUnscheduled visits will serve as extra study visits, if needed

cElectrocardiogram required for subjects >50 years old or with diabetes duration >20 years

dCollect only if subject is not extending their participation into the pivotal study

eDocumentation only applicable if there are changes from previous assessment

fVisits identified as "T/O" can either be conducted in person at the clinical site or over the telephone. Visits identified as "O" can only be conducted in person at the clinical site

gStudy device training for the CGM, blood glucose and ketone meters

hStudy device training for the Omnipod Horizon™ System

iSubjects deemed exempt from wearing the study CGM for 14-days will be eligible to immediately commence the hybrid closed-loop phase and may skip visit ST2

jAssessment of CGM criteria during screening applies to current Dexcom G6 users only

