## **Enrollment**

Subjects who meet all eligibility criteria and have completed all screening assessments will continue to enrollment. A subject is enrolled in the study upon placement of the first study CGM. Subjects that do not meet the eligibility criteria will not continue in the study and will be considered screen failures.

If for any reason a subject is no longer eligible for the study after the standard therapy phase has commenced but prior to the commencement of the hybrid closed-loop phase, the subject will not continue in the prepivot study. No additional study assessments will be required. The reason for study exit will be clearly documented.

## 8 STANDARD THERAPY - PHASE 1

The standard therapy phase will commence after all standard therapy assessments are completed per **Visit 2** – see Table 2: Schedule of Assessments.

During the standard therapy phase, subjects will be asked to perform the following:

- Manage their diabetes at home per their usual routine
- Administer meal boluses per their usual dosing routine
- Change their sensor if a sensor fails, or as needed
- Calibrate their CGM, if required, per the manufacturer's instructions
- Monitor their capillary blood glucose (BG) per usual routine
- Give meal boluses. The timing of the bolus delivery will be per each subject's typical dosing routine.

Extending standard therapy past 14-days will not constitute a protocol deviation unless standard therapy extends past 30-days. If subjects extend beyond the 14-days, the most recent 14-days of data will be used in the endpoint analysis if the data meets the criteria defined for CGM use and data availability. If a subject enrolls into the pivotal study, data collected in the standard therapy phase will be used in the endpoint analyses for the pivotal study as the subject will not be required to repeat the standard therapy phase as part of the pivotal study.

The standard therapy phase will be customized depending on the following subject profile:

- Current Dexcom G6 users
- Non-G6 users
- Pump Naïve users

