## 9.9 Early Withdrawal

Any subject may withdraw early from the study at any time for any reason. Upon withdrawal, assessments will be performed following the Table 2: Schedule of Assessments. The investigator may also terminate a subject's participation in the study if it is in the best interest of the subject or if the Sponsor or local regulatory agency (e.g., FDA) terminates the study.

The Early Withdrawal visit will include:

- Review of concomitant medications
- Height
- Weight
- Assessment of vital signs
- Assessment of AEs since last visit
- Completion of questionnaires (see Table 3: Questionnaires for specific requirements by age group):
  - WHO-5
  - EQ-5D
  - T1DDS
  - DTSQc
  - Hypoglycemia Confidence Scale
  - HABS
  - PSQI
  - IDSS (T1)
  - SUS
  - PAID-(Teen, Child)
  - INSPIRE-(Adult, Youth, Parent)
  - Clarke
  - Human Factors (HF) Questionnaire
- Discontinuation of remote monitoring
- Return all study devices
- Complaints/device deficiencies such as occlusion alarms and system hazard alarms since last visit
- Device uploads for BG and ketone meter
- Data review by clinician

The reasons for withdrawal will be recorded, and the subject's participation in the study will end.

In the event of a subject's death during the study, the subject's participation will be considered terminated and the date of death will be used as the date of study exit.

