### **11.3.2 Reportable Adverse Events**

Adverse events will be assessed on an ongoing basis throughout the study. Adverse event reporting will begin at the start time of the standard therapy phase (i.e., insertion of the CGM sensor) and continue through the hybrid closed-loop phase until the subject's participation has ended. All adverse events must be followed until resolution, or until the AE has stabilized, or until the study has been completed.

Pre-existing medical conditions or symptoms observed prior to the start time of the standard therapy phase will not be recorded as an AE and should be collected in the subject's medical history. In the event there is a change (i.e., worsening) in the pre-existing medical condition or symptoms after enrollment meeting the criteria of a reportable adverse event, then an AE must be reported.

For this protocol, a reportable adverse event includes any untoward medical occurrence that meets one of the following criteria:

1. An SAE
2. An ADE unless excluded from reporting in Hypoglycemic Events and Hyperglycemic/Ketotic Events sections below
3. An AE occurring in association with a study procedure
4. An AE not related to a study device issue which leads to temporary or permanent discontinuation of the study device
5. An AE that affects the participant's ability to complete any study procedures
6. An AE for which a visit is made to a hospital emergency department
7. Hypoglycemic Events as defined below
8. Hyperglycemic/Ketotic Events as defined below.

Skin reactions from sensor or pod placement are only reportable if severe and/or required treatment.

For the purpose of this protocol, mild symptoms of hypoglycemia and hyperglycemia (i.e., clinically non-significant) or blood glucose values out of the normal range (whether or not they resulted in delayed meals or correction boluses) will not be reported as AEs unless determined to meet the reportable criteria in the Hypoglycemic Events and Hyperglycemic/Ketotic Events sections below.

All reportable AEs—whether volunteered by the participant, discovered by study personnel during questioning, or detected through physical examination, laboratory test, or other means—will be reported on an AE eCRF.

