### 5.4 ANALYSIS OF ADVERSE EVENTS

Safety summaries and analyses will be based on all subjects that are enrolled in the study (i.e., Intention to Treat analysis set). All adverse events reported over the course of the study will be summarized and tabulated by study phase (standard therapy or HCL), event category, seriousness, severity, and relationship to the study procedures and the investigational device. Except where indicated, a subject reporting the same adverse event more than once will be counted once when calculating the number and percentage of subjects with that particular event. Adverse Event outcomes will be assessed descriptively as opposed to inferentially.

Adverse events leading to death or to discontinuation from the study will be listed separately. A listing of all adverse events will be provided. No formal tests of hypotheses are proposed for the safety endpoints.

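### Protocol 7.1 waives all further assessments for subjects who lose eligibility during standard therapy, while Table 2 note a and section 9.9 give them an Early Withdrawal visit with the only routine scheduled adverse event query they would have

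*Protocol*

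**What the plan says.** **Protocol 7.1, Enrollment.** The rule covers a subject who is no longer eligible, for any reason, "after the standard therapy phase has commenced but prior to the commencement of the hybrid closed-loop phase". That subject does not continue, and "No additional study assessments will be required". The reason for exit must be documented. Enrollment occurs when the first study CGM is placed.

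**Protocol Table 2, note a.** "Early withdrawal visit will only be conducted for any subjects that started but did not complete the full study"; the note goes on to define the full study as both phases. It makes no exception for loss of eligibility.

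**Protocol 9.9.** "Upon withdrawal, assessments will be performed following the Table 2: Schedule of Assessments". The section covers withdrawal by the subject and termination by the investigator. Its list includes "Assessment of AEs since last visit" and return of all study devices.

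**Protocol 11.3.2.** "Adverse event reporting will begin at the start time of the standard therapy phase", which it defines as sensor insertion. It also sets a general duty of ongoing AE assessment.

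**SAP 5.4.** "Safety summaries and analyses will be based on all subjects that are enrolled in the study". AEs are tabulated by phase, standard therapy or closed-loop.

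**The concern.** Two parts of the protocol give different instructions for what appears to be the same exit. A site following 7.1 closes the subject out with a reason code. A site following note a and 9.9 brings the subject back and asks about AEs. Both can say they complied, and they collect different safety data.

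This matters because the data lost are not collected at any other scheduled point. A subject who continues is asked about AEs at Visit 4. A subject who leaves before Visit 4 under 7.1 is never asked at a scheduled contact, over a period of 14 days as planned and up to 30 days without a deviation (Protocol section 8). That subject has been enrolled, AE reporting has been open since sensor insertion, and the ITT tables include the subject.

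**Working it through.** No figure in the plan can be reproduced here, because the sample size is not hypothesis-driven and no AE rate or pre-closed-loop dropout is stated. The check compares the texts and then puts an illustrative bound on the effect.

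**Step 1. Scheduled AE queries for a subject who exits before closed-loop**

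| Source | AE query? |
|---|---|
| Table 2, AE row, Visits 1 to 3 | None marked |
| Protocol 8.1 (Visit 2 list) | No AE item |
| Protocol 8.2 (Visit 3) | CGM criteria and an investigator judgment on safety concerns; no AE item |
| Table 2, AE row, Visits 4 to 10 | Marked, but not reached |
| Unscheduled visit | Marked, but held only if needed |
| Early Withdrawal visit (Table 2, 9.9) | Marked and listed |

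The routine scheduled count is 1 if the Early Withdrawal visit applies and 0 under 7.1.

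**Step 2. How an unqueried subject enters the tables**

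- ITT is all enrolled subjects (Protocol 12.3.1, SAP 7.1.1).
- AE tables by phase use ITT (SAP 5.4).
- Percentages use unique subjects as the denominator unless stated otherwise (Protocol 12.8).
- Available data only, with no imputation (Protocol 12.9, SAP 7.5).

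Together these count a subject with no AE record as having had no event. The documents do not say so in words; it follows from the four rules.

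**Step 3. Size, by assumption**

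Inputs: N = 48, the enrollment maximum (SAP 4.1). k, the number who exit this way with no AE query and no event recorded, is not stated. Event rates are assumed equal in queried and unqueried subjects.

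With x queried subjects having an event, the table reports x/48 and the rate among queried subjects is x/(48-k). The ratio is (48-k)/48.

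| k | (48-k)/48 | Unqueried share of ITT |
|---|---|---|
| 1 | 47/48 = 0.98 | 2.1% |
| 3 | 45/48 = 0.94 | 6.3% |
| 5 | 43/48 = 0.90 | 10.4% |
| 12 | 36/48 = 0.75 | 25% |

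k = 12 is 48 - 36, the whole allowance between enrolled and evaluable subjects. It is an extreme ceiling, because it sends every non-evaluable subject down this one route.

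Example with x = 4: at k = 3, the table shows 4/48 = 8.3% against 4/45 = 8.9%. At k = 12 it shows 8.3% against 4/36 = 11.1%.

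**Step 4. Chance that anything is missed**

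With an assumed per-subject AE rate p, the chance that at least one of k unqueried subjects had an event is 1 - (1-p)^k.

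| k | p = 2% | p = 5% | p = 10% |
|---|---|---|---|
| 3 | 1 - 0.98^3 = 6% | 1 - 0.95^3 = 14% | 1 - 0.90^3 = 27% |
| 12 | 1 - 0.98^12 = 22% | 1 - 0.95^12 = 46% | 1 - 0.90^12 = 72% |

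The rates p are assumptions; the documents give none for standard therapy.

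**The case against.** **Section 7.1 may be a deliberate exception.** It is specific, while 9.9 is general and does not name loss of eligibility. That reading is possible, but nothing in 7.1, note a or 9.9 states it, and note a on its plain wording includes these subjects. The SAP's precedence clause (SAP section 1) does not settle it, because the SAP says nothing about this visit.

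**A reader might infer that events are recorded only if the subject volunteers them.** The documents do not support that. Section 11.3.2 requires ongoing assessment and covers events found by questioning, examination or laboratory test. What 7.1 removes is the scheduled query.

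**A reader might infer that an event causing the exit would disappear.** That is not supported either. Section 7.1 requires the exit reason to be documented, section 8.2 has the investigator judge safety before closed-loop, and SAP 5.4 lists AEs leading to discontinuation separately. Those are the events most likely to be seen. At risk are reportable events unrelated to the exit.

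**A reader might infer that the safety endpoints are biased.** They are not affected. SAP 3.1 defines them during closed-loop, and SAP 7.1.2 uses mITT, which requires entry into closed-loop.

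**A reader might treat the 36 evaluable subjects as the only ones queried and compute 36/(36+k).** That equates non-evaluable with unassessed. A subject who enters closed-loop and later becomes non-evaluable was asked at Visit 4.

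**The exposed group is probably small.** Exempt Dexcom G6 users can go straight to closed-loop, and Group 1 (16 of the 36) is expected to consist only of G6 users. A subject who leaves before any study CGM is placed is not enrolled and not in ITT. This stands, and it argues for small k.

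**Conclusion.** The point holds as an unreconciled conflict between 7.1 on one side and Table 2 note a with 9.9 on the other. Its consequence is limited: following 7.1, enrolled subjects who exit in standard therapy have no routine scheduled AE query, yet they stay in the denominator of descriptive ITT AE tables. The tables affected are mainly the standard therapy ones, before the investigational system is dispensed.

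For a few exits the understatement is modest, at 0.98 to 0.90 of the true percentage for k = 1 to 5. This rests on 48 enrolled, equal event rates, and no event in the exiting subjects reaching the record by another route. If exit-causing events are recorded, as they should be, the shortfall is smaller.

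Severity is minor to moderate. It is worth correcting because the remedy is cheap and the missing data cannot be recovered later.

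**What to change.** State one rule in all four places.

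1. **7.1 and 8.2.** Replace the waiver in 7.1, and extend the exit paragraph in 8.2, with: *Any enrolled subject who exits before closed-loop, for any reason, will have an exit AE query covering the period since sensor insertion. Study devices will be returned and the reason for exit recorded.* The look-back should be explicit, because 9.9 asks only about the time since the last visit and Visits 2 and 3 carry no AE item.
2. **Table 2 note a and 9.9.** Refer to that rule, and say which other Early Withdrawal items apply to these exits: questionnaires, height, weight, vital signs and concomitant medications. For concomitant medications, also align 9.9, which lists the review, with the Table 2 row, which appears unmarked for Early Withdrawal. Changing 7.1 alone would leave a third version of the exit.
3. **SAP 5.4.** Report with the AE tables how many ITT subjects left before closed-loop, and how many of those had no AE query.

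The cost is a wording amendment in four places, one added line in the safety tables, and one short contact per exit. The protocol already provides the visit, and devices dispensed at Visit 2 have to be recovered in any case.

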### Current Dexcom G6 Users

Current Dexcom G6 users will be required to participate in the assessments required as part of standard therapy but may be exempt from wearing the study CGM for 14-days if the following criteria are met:

- Willing to provide 14-days of CGM data from the past 30-days
- Meet the success criteria of 80% CGM use during any consecutive 14-days in the past 30-days
- Must have  $\geq 2,016$  CGM values during the 14-days

If exemption criteria are not met, subjects may choose to continue to collect data until they meet the criteria or will be required to participate in the entire 14-day standard therapy phase consistent with the requirements for non-G6 users.

Subjects deemed exempt from wearing the study CGM for 14-days will be eligible to immediately commence the hybrid closed-loop phase.

### Non-G6 Users

All non-G6 users will be required to participate in the entire 14-day standard therapy phase. At the commencement of the standard therapy phase, subjects will be dispensed a CGM receiver that will be blinded and all user settable CGM alerts will be turned off. The device will record continuous glucose information over the 14-day period.

### **Pump Naïve Users**

Subjects who are naïve to pump therapy will have the opportunity to participate in a saline trial during the standard therapy phase. A saline trial consists of wearing a cleared Omnipod® DASH System with the Pod filled with saline to simulate pump therapy. This would enable subjects to familiarize themselves with the basic concepts of basal and bolus insulin delivery as well as provide the experience of wearing an on-body device prior to their participation in the hybrid closed-loop phase, if they choose to do so. This is optional and not required.

#### **8.1 Visit 2**

**Visit 2** represents the commencement of the standard therapy phase. All scheduled assessments will be performed according to Table 2: Schedule of Assessments. This visit will include:

- Review of concomitant medications
- Average total daily insulin (approximately over the past 7 days)
- Average total daily basal insulin (approximately over the past 7 days)
- Average total daily bolus insulin (approximately over the past 7 days)
- Review pump settings/MDI dosing
- Completion of questionnaires (see Table 3: Questionnaires for specific requirements by age group):
  - WHO-5
    - Used to measure current mental well-being
  - EQ-5D
    - Used to measure quality of life
  - T1DDS
    - Used to measure four critical dimensions of distress
  - DTSQs
    - Used to measure satisfaction with diabetes treatment regimens
  - Hypoglycemia Confidence Scale
    - Used to measure hypoglycemia unawareness, hypoglycemia frequency, severity and impact
  - HABS
    - Used to measure critical dimensions of hypoglycemia related concerns and confidence
  - PSQI
    - Used to measure sleep disturbance and usual sleep habits
  - IDSS (T1)
    - Used to measure patient satisfaction with their devices and impact on quality of life
  - SUS

- Used to measure usability of a system
- PAID-(Teen, Child)
  - Measures diabetes-related burden
- Training on Glucagon administration and information on treatment of hypo/hyperglycemia
  - All subjects are required to have access to glucagon and receive training on how to deliver the medication
- Study device training per manufacturer's instructions (CGM - blinded, BG, and ketone meters)
- Dispensing of CGM (blinded for non-G6 users), BG, and ketone meter
- QC testing of BG and ketone meter
  - Must pass at least one level of quality control testing prior to dispensing
- CGM sensor placement (if applicable)
  - Approved anatomical locations for CGM sensor placement will be reinforced as well as the importance of using approved locations

During this visit, subjects will be dispensed the following supplies:

- Dexcom transmitter
- Dexcom receiver
- Dexcom sensors
- Contour® Next One blood glucose meter
- Contour® Next One blood glucose meter test strips
- Contour® Next One blood glucose meter control solution
- Lancets
- Precision Xtra blood ketone meter
- Precision Xtra blood ketone meter test strips
- Precision Xtra blood ketone meter control solution

Subjects will be provided, by the site, information regarding treatment of hypoglycemia and hyperglycemia including sick day management and emergency management of severe hypoglycemia and diabetic ketoacidosis. Subjects will be given contact information for study personnel and product support.

If a subject is on MDI, the investigator will advise the subject on the treatment regimen to reduce insulin depending on the insulin action profile of injected doses prior to the commencement of the hybrid closed-loop phase. MDI subjects will be required to keep a log to record daily doses of insulin during the standard therapy phase.

## 8.2 Visit 3

**Visit 3** will be conducted in person at the clinical study site one (1) day prior to the start of the hybrid closed-loop phase. All scheduled assessments will be performed according to Table 2: Schedule of Assessments. This visit will include assessment of whether subjects have met the CGM usage and data criteria.

Prior to the commencement of the hybrid closed-loop phase, subjects must meet the following criteria:

- At least 80% CGM use (11.2-days) during any consecutive 14-days in the past 30-days and
- $\geq 2,016$  CGM values during the 14-days

If the CGM criteria is not met, the standard therapy phase may be extended, per investigator discretion, or the subject may be withdrawn from the study. At the conclusion of the standard therapy phase, if the investigator determines that there have been no safety concerns, the subject will continue to the hybrid closed-loop phase. If the investigator determines that it is unsafe for the subject to continue into the hybrid closed-loop phase, the subject will not be allowed to continue in the second phase of the study, and the reason for study exit will be documented.

## 9 HYBRID CLOSED-LOOP - PHASE 2

The hybrid closed-loop phase will commence at **Visit 4** upon the conclusion of the standard therapy phase and after all assessments are performed according to Table 2: Schedule of Assessments.

During the hybrid closed-loop phase, subjects will be asked to do the following:

- Adjust pump and CGM parameters to optimize their insulin therapy in collaboration with the recommendations from the clinical study staff
- Follow their pre-exercise management such as insulin reduction for meal boluses, consumption of snacks, or adjusting their insulin delivery settings
- Treat themselves per their usual routine if they become hypoglycemic or hyperglycemic or have symptoms of either at any time during the study
- Consume meals and snacks of their own choosing. Subjects will be encouraged to estimate the grams of carbohydrates for each meal or snack per their usual routine. The estimate should be entered into the meal bolus calculator.
- Administer meal boluses per their usual dosing routine
- Participate in target BG challenges as specified
- Change their CGM per manufacturer's instructions or sooner if necessary
- Change the Pod at least once every 72 hours
- Complete questionnaires (Table 3: Questionnaires)

Subjects will have scheduled follow-up visits according to Table 2: Schedule of Assessments and complete questionnaires according to Table 3: Questionnaires. Visits will be conducted either in the hotel/rental house environment, in person at the clinical study site or over the telephone. Subjects may also choose to use email or text as a substitute for their scheduled telephone visit.

The duration of the hybrid closed-loop phase will last 14-days.

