## 7 SCREENING AND ELIGIBILITY

Potential subjects for this study will include individuals who have been diagnosed with type 1 diabetes for at least 6 months and are appropriate for pump therapy per investigator's assessment. Potential subjects will be selected at each clinical study site and screened accordingly. Clinical study sites will be advised to:

- Recruit subjects using insulin aspart, lispro, and glulisine also known as Humalog, Novolog, Admelog, and Apidra
- Recruit at least 20% of subjects using MDI

Every effort will be made to establish eligibility of the patient prior to enrollment. Only patients who appear to meet all eligibility criteria will be enrolled in the study. Subject eligibility will be confirmed by study staff during a screening visit at the clinical site. Blood draws will be collected as required to demonstrate study eligibility as noted below. Laboratory results within the last 6 months, with the exception of A1C, may also be used if available.

Subjects that have participated in the prepivotal study may be eligible to extend their participation into the pivotal study.

### 7.1 Visit 1

Visit 1 will be conducted in person at the clinical study site. This visit will assess eligibility and will include:

- Signing of informed consent/assent
- Review of inclusion/exclusion criteria
- Screening assessments performed following Table 2: Schedule of Assessments
- Enrollment

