### 7.4 CALCULATION OF PERCENTAGE OF TIME IN RANGE

Several effectiveness endpoints involve calculation of percentage of time in a specific glycemic range. These endpoints will be based on the direct output from a device (either a CGM or The Omnipod Horizon™ Automated Glucose Control System). The percentage of time in range (TIR) will be calculated as:

$$100 \times \frac{\text{\# of CGM records in range}}{\text{\# of evaluable CGM records}} = \text{TIR\%}$$

The following CGM records will be excluded from analysis, and therefore, from calculation of TIR endpoints:

- No glucose value is provided in the device output, such as due to an error or device deficiency during which the device does not record glucose readings
- CGM records reported prior to start of standard therapy phase or after subject's discontinuation from HCL

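### For MDI subjects whose baseline CGM is collected prospectively, the insulin reduction advised before closed-loop can fall inside the standard therapy window, and no rule removes it

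*Protocol*

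**What the plan says.** Protocol section 8 defines the comparator condition. During ST, subjects are asked to "Manage their diabetes at home per their usual routine", and Protocol 5.2 adds that non-G6 users stay on their current MDI or pump therapy while wearing the blinded study CGM.

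Protocol 8.1 (Visit 2) says that for a subject on MDI "the investigator will advise the subject on the treatment regimen to reduce insulin depending on the insulin action profile of injected doses", and the sentence runs on to "prior to the commencement of the hybrid closed-loop phase. MDI subjects will be required to keep a log to record daily doses of insulin". The log covers the ST phase. The section gives no amount, start or duration for the reduction.

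Three provisions set the baseline window:

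- Protocol section 9 starts HCL at Visit 4 "upon the conclusion of the standard therapy phase and after all assessments are performed", so no gap is planned between the phases.
- Protocol section 8 says: "If subjects extend beyond the 14-days, the most recent 14-days of data will be used in the endpoint analysis", provided that the CGM criteria are met.
- SAP 7.4 removes records without a glucose value, "CGM records reported prior to start of standard therapy phase", and records after discontinuation from HCL. It removes nothing else.

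On who is affected, Protocol section 7 advises sites to "Recruit at least 20% of subjects using MDI" and sets no upper limit. Current G6 users who meet the data criteria may supply CGM data from the past 30 days and go straight to HCL (Protocol section 8).

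**The concern.** The primary endpoint compares each subject's TIR in HCL with the same subject's TIR in ST. The comparison is fair only if the ST records reflect the treatment that they are meant to represent. An insulin reduction advised by the study in preparation for the device is not usual routine, and it comes at the end of the period nearest HCL. For a prospectively monitored MDI subject, the plan as written lets those records count as standard therapy.

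All three primary comparisons (challenge days, non-challenge days, overall) use the same ST baseline, so any shift enters each of them. It also enters the baselines for the secondary glucose measures. No MDI-versus-pump analysis is specified, so the planned outputs would not reveal it.

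The baselines can also disagree with each other. SAP 6.4 takes baseline insulin from Visit 2, which covers roughly the preceding 7 days and so comes before the advised reduction. The glucose baseline for the same subject can include the reduction.

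Protocol section 8 carries the ST data of subjects who continue into the pivotal study's endpoint analyses, so the effect need not stay in this study.

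**Working it through.** The plan gives no effect size, SD or power calculation, so there is no planned figure for this bias to reproduce. The one related figure checks: 80% of 14 days = 0.80 × 14 = 11.2 days.

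**Who is exposed.** MDI subjects who wear the study CGM in the prospective phase, or G6 users still collecting data because they did not meet the exemption criteria. Exempt G6 users supply data already collected. Protocol 5.2 expects Group 1 (16 subjects) to consist solely of G6 users, so the exposed subjects should lie mainly in Group 2 (20 subjects).

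**Inputs from the documents.** Baseline of 14 days; 36 evaluable subjects; MDI minimum of 20%, that is 0.20 × 36 = 7.2, rounded up to 8.

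**Assumptions, not in the documents.** Reduction lasting 0.5 to 2 days inside the window; TIR 10 to 30 points lower during it; all 8 MDI subjects prospective.

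**Formulas.** Shift per affected subject = (affected days / baseline days with data) × TIR drop. Pooled shift = shift per subject × (number affected / 36).

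| Affected days | Baseline days | TIR drop | Per affected subject | Pooled, 8/36 |
|---|---|---|---|---|
| 0.5 | 14 | 10 | 0.36 | 0.08 |
| 1 | 14 | 20 | 1.43 | 0.32 |
| 2 | 14 | 30 | 4.29 | 0.95 |
| 2 | 11.2 | 30 | 5.36 | 1.19 |

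Results are also reported by age cohort (18 each). If all 8 fell in one cohort, the cohort shift would be 8/18 × 0.36 = 0.16 to 8/18 × 4.29 = 1.9 points. Because the MDI share has no cap, an outer case is all 20 Group 2 subjects affected: 20/36 × 4.29 = 2.4 points.

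**Direction.** Less insulin can move time from in range to above 180 mg/dL, which lowers baseline TIR, and from below 70 mg/dL into range, which raises it. The net change in TIR is the second amount minus the first. A net fall is the likelier result, but it can differ between subjects. For time below 70 and below 54 mg/dL the likely effect is a lower baseline, which understates any device benefit there.

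**The case against.** A reader might infer that every MDI subject's baseline TIR falls and that the device benefit is therefore overstated. The documents do not support that, for four reasons, all of which stand:

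- Exempt G6 users' baseline CGM largely predates the Visit 2 advice.
- Protocol 8.1 gives no duration. One adjusted dose near the switch-over would fit the text, and the timing clause could date the advice rather than the reduction.
- The sign for TIR is not fixed, and for the low-glucose endpoints the bias probably runs the other way.
- For subjects who do not extend, neither document states the last baseline record. Visit 3, where the CGM criteria are checked, comes one day before HCL, so a short reduction could fall partly or wholly outside the data used.

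The last point narrows the claim to possible inclusion, but it also shows that the end of the window is undefined. Where the phase is extended, the rule does keep the days nearest HCL.

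It can also be said that nothing in this study turns on the result. SAP 2.5 sets no success criteria, and SAP 4.2 states no hypotheses and disclaims clinical claims. That limits the importance here, though paired tests at 5% are still planned. Reuse of the ST data in the pivotal study keeps the point alive, but the analysis rules of that study are not in these documents, so its effect there cannot be judged.

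**Conclusion.** The concern holds in a limited form. The plan can count a study-advised insulin reduction as standard therapy for MDI subjects who collect baseline CGM prospectively, and neither document has a rule that prevents it. This part rests on the text and is secure.

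Direction and size are less certain. The bias is probably towards the device for TIR, mean glucose and time above 180 mg/dL, and probably against it for time below 70 and 54 mg/dL. Under the assumed 0.5 to 2 days and 10 to 30 points, it is about 0.4 to 4.3 TIR points per affected subject and about 0.1 to 1.0 point pooled with 8 of 36 affected. It is slightly more if baseline data are sparse, and less if some MDI subjects are exempt G6 users or the reduction lasts only hours. Overall confidence is moderate. It is a cheap improvement to the comparator, not a threat to the study's conclusions.

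**What to change.** 1. Record the date, and the time if available, when the investigator-advised reduction begins, alongside the existing MDI dose log. The log alone is not enough: it is required to hold only daily doses, and ordinary MDI doses vary, so a lower dose in it need not mark the advised reduction.
2. State in SAP 7.4 and Protocol section 8 that the baseline window for these subjects ends before that point and uses the preceding 14 days, or the available days.
3. State how the 80% and 2,016-value criteria apply to a shortened window. Losing 2 of 14 complete days leaves 12 days, above 11.2, and at one record every 5 minutes 12 × 288 = 3,456 values. A subject already at 11.2 days would fall to 9.2, which misses 80% of 14 days, so a rule is needed.
4. Add a sensitivity analysis that includes the excluded records.
5. Reconcile the usual-routine and insulin-reduction passages for the purpose of defining the baseline. No change to the clinical instruction is proposed.

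The cost is one extra recorded date, a few lines in each document, a slightly shorter baseline for some MDI subjects, and possibly a slightly smaller reported benefit.
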